9.2. General Plan to Manage Safety Concerns

9.2.1. Eligibility Criteria

Eligibility criteria were selected to guard the safety of patients in this study. Results from the nonclinical toxicology studies with BGB-DXP593, as well as the nonclinical/clinical data from other SARS-CoV-2 neutralizing mAbs were considered. Patients with any history of a severe allergic reaction that has a reasonable risk of recurrence are excluded from the study (see Section 4.2 for the full list of exclusion criteria).

9.2.2. Safety Monitoring Plan

Safety will be evaluated in this study through the monitoring of all AEs, defined and graded according to NCI-CTCAE Version 5.0.

All enrolled patients will be evaluated clinically and with standard laboratory tests at regular intervals during their participation in this study. Safety evaluations will consist of medical interviews, recording of AEs (see Section 9.6), physical examinations, laboratory measurements (hematology, clinical chemistry, etc), and other assessments including those listed in Appendix 1.

Administration of the study drug will be performed in a setting where emergency medical equipment and staff who are trained to respond to medical emergencies are available (for additional information, see Section 5.2).

Blood samples will be drawn for determination of ADAs to BGB-DXP593 in patients who have received the study drug.

Investigators are instructed to report all AEs (includes pregnancy-related AEs).

The potential safety issues anticipated in this study, as well as measures intended to avoid or minimize such toxicities, are outlined in Section 9.7.

9.3. Adverse Events

9.3.1. Definitions and Reporting

An AE is defined as any unfavorable and unintended sign (including an abnormal laboratory finding), symptom, or disease (new or exacerbated) temporally associated with the use of a study drug, whether considered related to the study drug or not.

Examples of AEs include:

- Worsening of a chronic or intermittent pre-existing condition, including an increase in severity, frequency, duration, and/or has an association with a significantly worse outcome
- Detection or diagnosis of a new condition after study drug administration even though the condition might have been present before the start of the study
- Signs, symptoms, or the clinical sequelae of a suspected interaction
- Signs, symptoms, or the clinical sequelae of a suspected incorrect administration of either study drug or a concurrent medication

When an AE or SAE occurs, it is the responsibility of the investigator to review all documentation (eg, hospital progress notes, laboratory results, and diagnostics reports) relative to the AE or SAE. The investigator will then record all relevant information regarding an AE or SAE in the eCRF. However, there may be instances when copies of medical records for certain cases are requested by the sponsor. In this instance, all patient identifiers will be blinded on the copies of the medical records before submission to the sponsor.

9.3.2. Assessment of Severity

The investigator will assess the severity for each AE and SAE reported during the study. AEs and SAEs should be assessed and graded based upon NCI-CTCAE Version 5.0.

Toxicities that are not specified in NCI-CTCAE will be defined as follows:

- Grade 1: Mild; asymptomatic or mild symptoms; clinical or diagnostic observations only; intervention not indicated
- Grade 2: Moderate; minimal, local, or noninvasive intervention indicated; limiting age-appropriate instrumental activities of daily living
- Grade 3: Severe or medically significant but not immediately life-threatening; hospitalization or prolongation of hospitalization indicated; disabling; limiting self-care activities of daily living
- Grade 4: Life-threatening consequences; urgent intervention indicated
- Grade 5: Death related to AE

Note: The terms “severe” and “serious” are not synonymous. Severity is a measure of intensity (eg, grade of a specific AE, mild [Grade 1], moderate [Grade 2], severe [Grade 3], or life-threatening [Grade 4]); whereas, seriousness is classified by the criteria based on the regulatory definitions. Seriousness serves as the guide for defining regulatory reporting obligations from the sponsor to applicable regulatory authorities as described in Section 9.6.2.

9.3.3. Assessment of Causality

The investigator is obligated to assess the relationship between the study drug and the occurrence of each AE or SAE using best clinical judgment. Alternative causes, such as natural history of the underlying diseases, concomitant therapy, other risk factors, and the temporal relationship of the AE or SAE to the study drug should be considered and investigated. The investigator should consult the [BGB-DXP593 Investigator’s Brochure](#) in the determination of his/her assessment.

There may be situations when an SAE has occurred and the investigator has only limited information to include in the initial report to the sponsor. However, it is very important that the investigator always assesses causality for every SAE before transmission of the SAE report to the sponsor because the causality assessment is 1 of the criteria used when determining regulatory reporting requirements. The investigator may subsequently change his/her opinion of causality considering follow-up information and may amend the SAE report accordingly.

The causality of each AE should be assessed and classified by the investigator as “related” or “not related” based on all information available at the time of reporting. An AE is considered related if there is “a reasonable possibility” that the AE may have been caused by the study drug (ie, there are facts, evidence, or arguments to suggest possible causation). A number of factors should be considered in making this assessment, including:

- Temporal relationship of the AE to the administration of study treatment/study procedure
- Whether an alternative etiology has been identified
- Mechanism of action of the study drug
- Biological plausibility
- An AE should be considered “related” to study drug if any of the following criteria are met; otherwise, the event should be assessed as “not related”:
 - There is clear evidence to suggest a causal relationship, and other possible contributing factors can be ruled out
 - There is evidence to suggest a causal relationship, and the influence of other factors is unlikely
 - There is some evidence to suggest a causal relationship (eg, the AE occurred within a reasonable time after administration of the study drug). However, the influence of other factors may have contributed to the AE (eg, the patient’s clinical condition or other concomitant AEs).

9.3.4. Follow-up of Adverse Events

After the initial AE or SAE report, the investigator is required to proactively follow each patient and provide further information to the sponsor on the patient's condition.

All AEs and SAEs documented at a previous visit/contact and designated as ongoing will be reviewed at subsequent visits/contacts.

All AEs and SAEs will be followed until resolution, the condition stabilizes or is considered chronic, the AE or SAE is otherwise explained, the patient is lost to follow-up, or the patient withdraws consent. The investigator will ensure that follow-up includes any supplemental investigations as may be indicated to elucidate the nature and/or causality of the AE or SAE. This may include additional laboratory tests or investigations, histopathological examinations, radiographic imaging, or consultation with other health care professionals.

The sponsor may request that the investigator perform or arrange for the conduct of supplemental measurements and/or evaluations to elucidate as fully as possible the nature and/or causality of the AE or SAE. The investigator is obligated to assist. If a patient dies during participation in the study or during a recognized follow-up period, the sponsor will be provided with a copy of any postmortem findings, including histopathology.

New or updated information should be reported to the sponsor according to the SAE instructions provided by the sponsor within the timeframes outlined in Section 9.6.2.

9.3.5. Laboratory Test Abnormalities

Abnormal laboratory findings (eg, clinical chemistry, complete blood count, coagulation, or urinalysis) or other abnormal assessments (eg, ECGs or vital signs) that are judged by the investigator as clinically significant will be recorded as AEs or SAEs. This includes clinically significant abnormal laboratory findings or other abnormal assessments that are present at baseline and significantly worsen during the study. The definition of clinically significant is left to the judgment of the investigator. In general, these are the laboratory test abnormalities or other abnormal assessments that:

- are associated with clinical signs or symptoms, or
- require active medical intervention, or
- lead to treatment interruption or discontinuation, or
- require close observation, more frequent follow-up assessments, or further diagnostic investigation.

If a clinically significant laboratory abnormality is a sign of a disease or syndrome (eg, alkaline phosphatase and bilirubin 5 x ULN associated with cholestasis), only the diagnosis (ie, cholestasis) should be recorded on the AE eCRF.

If the laboratory abnormality can be characterized by a precise clinical term per standard definitions, the clinical term should be recorded as the AE. For example, an elevated serum potassium level of 7.0 mEq/L should be recorded as "hyperkalemia."

Observations of the same clinically significant laboratory abnormality from visit to visit should not be repeatedly recorded on the AE eCRF, unless the etiology changes. The initial severity of the event should be recorded, and the severity or seriousness should be updated any time the event worsens.

9.4. Definition of a Serious Adverse Event

An SAE is any untoward medical occurrence that, at any dose:

- Results in death
- Is life-threatening

Note: The term “life-threatening” in the definition of “serious” refers to an AE in which the patient was at risk of death at the time of the AE. It does not refer to an AE that hypothetically might have caused death if it was more severe.

- Requires hospitalization or prolongation of existing hospitalization

Note: In general, hospitalization signifies that the patient was admitted (usually involving at least an overnight stay) to the hospital or emergency ward for observation and/or treatment that would not have been appropriate in the physician’s office or outpatient setting.

- Results in disability/incapacity

Note: The term “disability” means a substantial disruption of a person’s ability to conduct normal life functions. This definition is not intended to include experiences of relatively minor medical significance, such as uncomplicated headache, nausea, vomiting, diarrhea, influenza, and accidental trauma (eg, sprained ankle), which may interfere with or prevent everyday life functions but do not constitute a substantial disruption.

- Is a congenital anomaly/birth defect
- Is considered a significant medical AE by the investigator based on medical judgement (eg, may jeopardize the patient or may require medical/surgical intervention to prevent one of the outcomes listed above)

The following are NOT considered to be SAEs:

- Hospitalization for elective treatment of a pre-existing condition that did not worsen from baseline
- Hospitalization for social/convenience considerations
- Scheduled therapy for the target disease of the study, including admissions for PK sampling or convenience

9.5. Suspected Unexpected Serious Adverse Reaction

A suspected unexpected serious adverse reaction is a serious adverse reaction that is both unexpected (ie, not present in the study drug’s reference safety information) and meets the definition of a serious adverse drug reaction, the specificity or severity of which is not consistent with those noted in the [BGB-DXP593 Investigator’s Brochure](#).

9.6. Timing, Frequency, and Method of Capturing Adverse Events and Serious Adverse Events

9.6.1. Adverse Event Recording Period

After informed consent has been signed but before the administration of the study drug, only SAEs should be reported.

After initiation of the study drug, all AEs and SAEs, regardless of relationship to study drug, will be reported until 30 days after study treatment or End-of-Study Visit, whichever is later. After the period, the investigator should report any SAEs that are considered to be related to the study drug.

For the follow-up period for AEs, see Section [9.3.4](#).

9.6.2. Reporting Serious Adverse Events

9.6.2.1. Prompt Reporting of Serious Adverse Events

As soon as the investigator determines that an AE meets the protocol definition of an SAE, the event must be reported promptly (within 24 hours) to the sponsor or designee as described in [Table 2](#).

Table 2: Timeframes and Documentation Methods for Reporting Serious Adverse Events to the Sponsor or Designee

	Timeframe for sending initial report	Documentation method	Timeframe for sending follow-up report	Documentation method	Reporting method
All SAEs	Within 24 hours of first knowledge of the SAE	SAE report	As expeditiously as possible	SAE report	Email or fax SAE report form

Abbreviations: SAE, serious adverse event.

9.6.2.2. Completion and Transmission of the Serious Adverse Event Report

Once an investigator becomes aware that an SAE has occurred in a patient, he/she is to report the information to the sponsor within 24 hours, as outlined above in Section [9.6.2.1](#). The SAE report will always be completed as thoroughly as possible, including all available details of the event and forwarded to the sponsor or designee within the designated timeframes.

If the investigator does not have all information regarding an SAE, he/she is not to wait to receive additional information before notifying the sponsor or designee of the SAE and completing the form. The form will be updated when additional information is received.

The investigator must always provide an assessment of causality for each SAE as described in Section 9.3.3.

The sponsor will provide contact information for SAE receipt.

9.6.2.3. Regulatory Reporting Requirements for Serious Adverse Events

The investigator will report all SAEs to the sponsor in accordance with the procedures detailed in Section 9.6.2.1. The sponsor has a legal responsibility to notify, as appropriate, both the local regulatory authority and other regulatory agencies about the safety of a drug under clinical investigation.

The investigator, or responsible person according to local requirements, will comply with the applicable local regulatory requirements related to the reporting of SAEs to regulatory authorities and the IRB/IEC.

All suspected unexpected serious adverse reactions (as defined in Section 9.5) will be submitted to all applicable regulatory authorities and investigators for BGB-DXP593 studies.

When a study center receives an initial or follow-up safety report or other safety information (eg, revised Investigator's Brochure) from the sponsor, the investigator or designated responsible person is required to promptly notify his/her IRB or IEC. The investigator should place copies of safety reports from the sponsor in the investigator site file.

9.6.3. Eliciting Adverse Events

The investigator or designee will ask patients about AEs by asking the following standard questions:

- How are you feeling?
- Have you had any medical problems since your last visit?
- Have you taken any new medicines since your last visit?

9.6.4. Deaths

Death is an outcome and not usually considered an AE. If the only information available is death and the cause of death is unknown, then the death is reported as an AE (eg, "death," "death of unknown cause," or "death unexplained").

9.6.5. Recording Pregnancies

If a female patient or the partner of a male patient becomes pregnant within 30 days after the single dose of study drug, a pregnancy report form must be completed and expeditiously submitted to the sponsor to facilitate outcome follow-up. Information on the status of the mother and child will be forwarded to the sponsor. Generally, follow-up will be no longer than 6 to 8 weeks following the estimated delivery date. Any premature termination of the pregnancy will be reported.

While pregnancy itself is not considered to be an AE, any pregnancy complication or elective termination of a pregnancy for medical reasons will be recorded as an AE or SAE.

An abortion, whether accidental, therapeutic, or spontaneous, should always be reported as an SAE. Similarly, any congenital anomaly/birth defect in a child born to a patient exposed to the study drug should be recorded and reported as an SAE.

9.6.6. Expedited Reporting to Health Authorities, Investigators, Institutional Review Boards, and Independent Ethics Committees

The sponsor will promptly assess all SAEs against cumulative study drug experience to identify and expeditiously communicate new safety findings to regulatory authorities, investigators, IRBs, and IECs based on applicable legislation.

To determine the reporting requirements for individual SAEs, the sponsor will assess the expectedness of the SAEs using the following reference safety information documents:

- [BGB-DXP593 Investigator's Brochure](#)

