4.1. Inclusion Criteria

Each patient must meet all of the following inclusion criteria to be considered eligible for participation in this study:

1. Participant must be at least 18 years of age at the time of signing the informed consent.
2. Laboratory-confirmed SARS-CoV-2 infection (positive reverse transcription-polymerase chain reaction [RT-PCR] test or other testing methods authorized by local regulatory authorities) in any samples following local practice ≤ 72 hours prior to screening
3. Have experienced COVID-19 symptoms for ≤ 7 days prior to treatment assignment, such as fever, cough, shortness of breath, sore throat, diarrhea, vomiting, and dysgeusia
4. Agree to the collection of nasopharyngeal swabs, saliva, and venous blood
5. Female patients of childbearing potential must be willing to use a highly effective method of birth control (see [Appendix 4](#)) from the time of study enrollment until 4 months after the study dosing
6. Male patients with female partners of childbearing potential must be willing to use a highly effective method of birth control (see [Appendix 4](#)) from the time of study enrollment until 4 months after the study dosing
7. Able to provide written informed consent and can understand and agree to comply with the requirements of the study and the schedule of assessments

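### The pregnancy report form and outcome follow-up cover only pregnancies that begin within 30 days of dosing, although contraception is required for 4 months

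*Protocol*

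**What the plan says.** Inclusion criteria 5 and 6 (Protocol Section 4.1) require highly effective birth control from female patients of childbearing potential, and from male patients whose female partners are of childbearing potential, "from the time of study enrollment until 4 months after the study dosing".

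Protocol Section 9.6.5 asks for a pregnancy report form, so that the outcome can be followed, when a female patient or a male patient's partner "becomes pregnant within 30 days after the single dose of study drug". No other section extends that window.

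Section 9.6.5 also sets rules for events during a pregnancy and states no time limit for them:
- The pregnancy alone does not count as an adverse event: "While pregnancy itself is not considered to be an AE".
- Complications, and terminations done on medical grounds, go on record as AEs or SAEs.
- Every abortion counts as serious: "An abortion, whether accidental, therapeutic, or spontaneous, should always be reported as an SAE".
- An SAE report is required for "any congenital anomaly/birth defect in a child born to a patient exposed to the study drug".

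Under Section 9.6.1, all AEs and SAEs are collected until 30 days after treatment or the End-of-Study Visit, whichever is later. After that, only SAEs judged related to study drug are requested. Section 9.3.4 adds that "All AEs and SAEs will be followed until resolution", or until another listed end point such as stabilisation or loss to follow-up.

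**The concern.** The protocol treats the 4 months after dosing as a time when pregnancy should be avoided, yet it actively follows outcomes only for pregnancies that begin in the first 30 days. What is at stake is fetal safety information on a new antibody. Section 9.1 states that no clinical data are available yet, and Section 1.2.1.2 describes no reproductive or developmental toxicity study. The Investigator's Brochure was not available to check that point.

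The protocol gives no exposure-based reason for stopping at 30 days. Section 1.3.1 predicts lung concentrations above the IC99 over 29 days at 5 mg/kg and higher doses, and Appendix 2 still samples for drug at Day 113.

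Sample size, power and the primary analysis are not involved.

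**Working it through.** The plan gives no figure of its own to reproduce, so the check compares the stated windows and traces what happens to a pregnancy in the gap.

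**Inputs**
- Form window: 30 days after dosing (Protocol 9.6.5).
- Contraception: until 4 months after dosing (Protocol 4.1).
- Month length: 30.4375 days (SAP 6.2.2).
- Last planned visit: Day 113, listed in Protocol Appendix 2 as 2688 hours after the start of infusion, with a window of ±7 days (Protocol 8.6).

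**Length of the gap**
- Contraception period: 4 × 30.4375 = 121.75 days.
- Outside the form window: 121.75 − 30 = 91.75 days.
- Share inside the form window: 30 / 121.75 = 24.6%.
- With months of 28 to 31 days, the period is 112 to 124 days, the uncovered part is 82 to 94 days, and the covered share is 26.8% to 24.2%.

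**Where the gap falls relative to the last visit**

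| Last visit | Days after dosing | Gap before the visit | Gap after the visit |
|---|---|---|---|
| Earliest allowed | 112 − 7 = 105 | 105 − 30 = 75 | 121.75 − 105 = 16.75 |
| Planned Day 113 | 2688 / 24 = 112 | 112 − 30 = 82 | 121.75 − 112 = 9.75 |
| Latest allowed | 112 + 7 = 119 | 119 − 30 = 89 | 121.75 − 119 = 2.75 |

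**How far such a pregnancy can have progressed by the last visit**

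A pregnancy that begins just after day 30 is at most 82 / 7 = 11.7 weeks past conception at planned Day 113. Across the visit window this is 75 / 7 = 10.7 to 89 / 7 = 12.7 weeks. Its birth outcome therefore comes after the last scheduled contact.

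**What the protocol triggers for a pregnancy that begins after day 30 and within 4 months**
- *Form and outcome follow-up:* none, because the 30-day condition is not met.
- *AE follow-up while uncomplicated:* none. Section 9.6.5 says pregnancy is not an AE, and the follow-up in Section 9.3.4 is for AEs and SAEs.
- *Complication, medical termination or abortion:* reportable as an AE or SAE. Up to the End-of-Study Visit this applies regardless of relationship to drug. Later, it is unclear whether Section 9.6.1's limit to drug-related SAEs also restricts Section 9.6.5.
- *Birth defect:* an SAE, but the report depends on the site hearing of it, since no contact is scheduled then.
- *Detection up to Day 113:* visit questions (Section 9.6.3) and pregnancy tests after screening (Appendix 1) can reveal the pregnancy. The test days cannot be read reliably from the extracted table. A positive test for a pregnancy that began after day 30 would still require no form.
- *Partners of male patients:* cover is thinner. The scheduled tests are for women of childbearing potential, whom Appendix 4 defines as female patients, and the birth-defect sentence in Section 9.6.5 refers to a child born to a patient.

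A pregnancy that begins by day 30 and is discovered later does get the form, so the limit concerns when the pregnancy starts, not when it is found.

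**The case against.** The strongest reply is that nothing is contradictory. Contraception is a precaution and the form is a reporting trigger, and no text says their windows must match. The protocol does not explain the 4 months. They may simply span participation, since the latest End-of-Study Visit is 119 days after dosing against about 122 days. The 30 days also matches the TEAE window in Section 10.3.2.

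Existing cover is substantial. For patients who complete the study, all AEs and SAEs are collected to about Day 113, which takes in about 82 of the 92 days. Section 9.4 lists congenital anomaly as an SAE criterion without the narrower wording of Section 9.6.5. Section 9.6.5 also asks for premature terminations to be reported, although that sentence sits with the form and its reach past 30 days is arguable. A complication, once recorded, is followed to resolution or stabilisation.

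The antibody targets a viral protein. The toxicology section reports no specific binding to normal human or monkey tissue and no treatment-related findings in monkeys up to 300 mg/kg.

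Much of this stands. It makes the point an improvement to a stated choice rather than the correction of an error, and it narrows what is missed. It does not close the gap: an uncomplicated pregnancy that begins after day 30 starts no follow-up, and its birth outcome is known only if someone tells the site. The TEAE window is a weak defence because it governs tabulation, while AE collection itself runs to the End-of-Study Visit. The toxicology findings bear on how worried to be, but they include no described reproductive study.

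**Conclusion.** The concern holds. Followed as written, the form and outcome follow-up cover about 25% of the post-dose contraception period, and about 92 days are left out (82 to 94 days, depending on month length). What is missed is narrow: uncomplicated pregnancies that begin after day 30, outcomes after the End-of-Study Visit that the site does not hear about, and some events in partners of male patients.

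These figures are calendar lengths, not risks or expected counts. The documents give no pregnancy rate, and few pregnancies are likely among about 172 patients who must agree to contraception. The conclusion assumes the SAP's month length and that the 4 months run from the dose. It does not rest on the pregnancy-test days in Appendix 1. The change should be made as an inexpensive fetal-safety improvement.

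**What to change.** In Protocol Section 9.6.5, change the limit in "becomes pregnant within 30 days after the single dose of study drug" from 30 days to 4 months, for female patients and for partners of male patients. The form would then cover the whole post-dose contraception period instead of about a quarter of it.

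The edit is one phrase, but Section 14.2.1 requires an amendment submitted to competent authorities and IRBs/IECs, possibly with a revised consent form, across about 20 to 30 sites. A few more forms and outcome contacts after Day 113 may follow.

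The change has limits. Pregnancies that begin in roughly the last 10 days, after the planned Day 113 visit, would still come to light only if the patient tells the site. Partners would still not be tested. The birth-defect wording and the unclear relation to Section 9.6.1 would also remain, and could be tidied in the same amendment.
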